4. OBJECTIVE(S)/SPECIFIC AIMS AND HYPOTHESES

- A concise statement of the goal(s) of the current study.
- *The rationale for and specific objectives of the study.*
- The goals and the hypothesis to be tested should be stated.

Aim 1: Evaluate the effectiveness of a search engine ad campaign on reducing DUP and raising rates of FEP referrals by directly comparing DUP and FEP referrals pre-campaign to DUP and FEP referrals during the campaign. Hypothesis A: Patients admitted to OTNY via campaign channels will demonstrate significantly shorter DUP than those admitted to OTNY through traditional outreach prior to campaign activation. Hypothesis B: Activating the campaign will significantly increase the number of FEP referrals and patients admitted to OTNY as compared to the number of FEP referrals and patients to OTNY admitted pre-campaign activation.

Version Date: 6.9.22 Page 6 of 31

Aim 2: Determine the efficacy of a campaign targeting caregivers in promoting treatment initiation by comparing rates of OTNY enrollment arriving through the caregiver campaign to rates of enrollment arriving through the patient campaign. Hypothesis: Engaging caregivers online will significantly increase the likelihood of promoting treatment initiation for individuals with FEP as compared to engaging prospective patients online. Aim 3: Explore which methods of online engagement are most effective at promoting treatment initiation by comparing rates of OTNY enrollment of individuals with FEP interacting with research staff via two-way video and live chat to rates of enrollment of individuals with FEP utilizing text, email, and/or phone alone. Hypothesis: Individuals with FEP who engage via two-way video and live chat will be significantly more likely to initiate in-person contact compared to individuals with FEP who engage via text, email, and/or phone alone.

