7. ELIGIBILITY CRITERIA

- Describe the characteristics of the subject population, including their anticipated number, age, ranges, sex, ethnic background, and health status. Identify the criteria for inclusion or exclusion of any subpopulation.
- Explain the rationale for the involvement of special classes of subjects, such as fetuses, pregnant women, children, prisoners or other institutionalized individuals, or others who are likely to be vulnerable. You cannot include these populations in your research, unless you indicate such in the protocol
- Similarly, detail exclusionary criteria: age limits, special populations (minors, pregnant women, decisionally impaired), use of concomitant medications, subjects with other diseases, severity of illness, etc.

Version Date: 6.9.22 Page 8 of 31

Given that ads will appear in response to any online search query conducted by any individual in NYS that align with the campaign's keywords, we will likely interact with many individuals searching for behavioral health information online. All campaign related inquiries will be recorded centrally by research staff. Individuals experiencing FEP will be referred to OTNY.

OTNY Inclusion criteria include: 1) DSM-V diagnosis of schizophrenia, schizophreniform, schizoaffective disorder, brief psychotic disorder, delusional disorder, unspecified schizophrenia spectrum disorder, assessed via clinical interview; 2) psychotic symptom onset within the past two years; 3) ages 16 to 30 years; 4) NYS resident

OTNY Exclusion criteria include: 1) diagnosis of substance-induced psychotic disorder, a psychotic disorder due to a general medical condition, or mood disorder with psychotic features; 2) Intellectual disability (IQ < 70) or autistic spectrum disorder assessed by clinical interview.

All individuals who meet OTNY inclusion criteria will be offered care regardless of insurance status or ability to pay. All ineligible OTNY referrals will be referred to appropriate local services.

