12. STATISTICAL ANALYSIS

- Describe how your data will be used to test the hypotheses.
- State clearly what variables will be tested and what statistical tests will be used.
- *Include sample size calculations.*
- If this is a pilot study, state which variables will be examined for hypothesis generation in later studies.

A stepped-wedge cluster randomization (CR) design will be implemented. After a baseline period of six months, two clusters (grouped clinics) will be randomly assigned in month 7 and by month 18, all of NYS will be running the campaign. This strategy allows each region to serve as its own control³⁷. The treatment effect can be modeled as a random effect at the cluster level which will accommodate treatment heterogeneity across the clinics. We grouped the 21 OTNY sites into 6 clusters based on geolocation as well as the total number of FEP referrals at each clinic between 10/01/2017 to 09/30/2018. We combined some regions to ensure that each cluster will be able to successfully meet recruitment criteria. The six clusters are; 1) Bronx, 2) Manhattan, 3) Queens, 4) Brooklyn, 5) Hudson River/Central NY, 6) Staten

Version Date: 6.9.22 Page 12 of 31

Island/Long-Island/Western NY. There will be a total of four 6-month time periods, including the baseline period where all 6 clusters receive the control treatment. All analyses for Aim 1 (hypotheses A and B) will be conducted within the Generalized Linear Mixed Models (GLMM) framework with an identity link for continuous outcomes and logit link for binary outcomes. Analyses for Aim 2 will be done using asymptotic z-tests for proportions after accounting for the variance inflation factors (VIF). Aim 3 is exploratory, and hence only 95% confidence intervals, accounting for VIFs, will be calculated for the rates.

Aim 1: Evaluate the effectiveness of a search engine ad campaign on reducing DUP and raising rates of FEP referrals by directly comparing DUP and FEP referrals pre and post campaign activation. Hypothesis A: Patients admitted to OTNY via campaign channels will demonstrate a significantly shorter DUP than those admitted to OTNY through traditional outreach prior to campaign activation.

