DUP will be defined as per Compton³⁶. DUP onset will be defined as the first full threshold delusion or hallucination, lasting throughout the day for several days or several times a week, not limited to a few brief moments. The endpoint will be defined as treatment with an antipsychotic (DUP 1). Given that our aim is to connect patients with specialty care, we will also define the DUP endpoint (DUP II) as enrollment in OTNY.

OTNY programs currently assess DUP at each site locally as part of the intake process. The mean DUP (n=1222) from symptom onset to OTNY enrollment is reported to be 7.6 months (median 5.5 months). For the duration of the award, all de-identified DUP data routinely uploaded to OTNY central (as part of standard quality improvement) will be provided to research staff for analyses. We will compare DUP from each site prior to activing the campaign, to DUP during the active phase of the campaign, arriving both through the campaign as well as through traditional channels.

Power Analysis: Sample size calculations were done using Hemming and Taljaard's second strategy³⁸ for stepped wedge CR design, where a fixed number of clusters (6) and number of steps (3) was specified based on feasibility, and the required number of participants per site per period was determined as the positive solution of a quadratic equation. In addition, intracluster correlation (ICC) for the sites was also required. Mean DUP reported from the RAISE-ETP study³ was 179 weeks (SD = 249), and the ICC used for the original power analysis for the RAISE study was 0.1. Prior marketing campaigns have reduced DUP substantially^{5,6}. Assuming a 50% reduction with our new intervention, the sample size required at 80% power and α = 0.05, is 32 participants per 6-month period per cluster, leading to (32 x 4 x 6=) 768 participants for Aim 1. Based on existing OTNY enrollment data, the Bronx will receive approximately 30 new intakes per 6-month period. In order to compensate, we will be collecting DUP data from 40 participants per 6months period in the Manhattan and Brooklyn clusters. Power analysis was done only for the primary outcome (hypothesis A).

Version Date: 6.9.22 Page 13 of 31

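### Aim 1's 80% power rests on an outside DUP (mean 179 weeks, SD 249) that cannot describe onset-to-enrolment DUP in OTNY, and the calculation appears to be for a different contrast from hypothesis A as worded

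*Combined protocol and SAP*

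**What the plan says.** Section 12 (Statistical Analysis), Aim 1, fixes six clusters and three steps, with four six-month periods. It takes its planning values from RAISE-ETP: mean DUP "was 179 weeks (SD = 249), and the ICC used for the original power analysis for the RAISE study was 0.1". With a 50% reduction, 80% power and α = 0.05, it arrives at 32 participants per cluster per period, 768 in all.

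The same section defines DUP in two ways. First: "The endpoint will be defined as treatment with an antipsychotic (DUP 1"). Then: "we will also define the DUP endpoint (DUP II) as enrollment in OTNY". It does not say which one the calculation serves. For the second it has local data: "The mean DUP (n=1222) from symptom onset to OTNY enrollment is reported to be 7.6 months (median 5.5 months"). No SD is given. Section 7 (Eligibility Criteria) limits OTNY to "psychotic symptom onset within the past two years".

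On the contrast, section 12 states: "Power analysis was done only for the primary outcome (hypothesis A"). Section 4 words hypothesis A as "Patients admitted to OTNY via campaign channels will demonstrate significantly shorter DUP than those admitted to OTNY through traditional outreach" before the campaign began. Section 12 also plans to compare each site's pre-campaign DUP with active-phase DUP from both campaign and traditional channels. On the model it says: "The treatment effect can be modeled as a random effect at the cluster level".

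**The concern.** The planning mean is more than five times OTNY's own (179 against 33 weeks), and the assumed fall exceeds the whole of OTNY's mean DUP. If DUP II is the powered outcome, the only power figure for the primary outcome describes a distribution that cannot occur in this programme. A reader of the result, particularly a null result, would not know what reduction the trial could have detected.

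A second mismatch would remain even with perfect DUP inputs. The power statement is labelled as hypothesis A, which is about patients arriving through campaign channels, but it uses the same count in every cell, control and active. Campaign arrivals are only part of active-phase intake.

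**Working it through.** **1. The plan's own figure.** Inputs (section 12): 6 clusters, 2 crossing at each of 3 steps, 4 periods, hence 12 control and 12 active cells; SD 249 weeks; ICC ρ = 0.1; fall 0.5 × 179 = 89.5 weeks. Sidedness is not stated; two-sided 0.05 reproduces the figure. Method: generalised least squares on cluster-period means, with fixed period effects and one random cluster effect. Each cluster's covariance matrix is diag[(1 − ρ)SD²/m] + ρSD²J, where m is the cell count and J the all-ones matrix. Power = Φ(fall/SE − 1.96).

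- At m = 32, SE = 0.1274 × SD = 31.7 weeks; 89.5/31.7 = 2.82; power 80.5%.
- At m = 31, power is 79.3%.

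So 32 is the smallest count reaching 80%, and 32 × 4 × 6 = 768. The arithmetic stands.

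**2. Can the inputs describe DUP II?** Take the onset limit to hold at enrolment and 1 month = 4.348 weeks.

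- Maximum DUP II: 24 months = 104.4 weeks, below the assumed mean of 179.
- A variable confined to 0–104.4 has SD at most 104.4/2 = 52.2 weeks; 249/52.2 = 4.8.
- If the limit is judged at referral and enrolment follows up to 6 months later (assumed), the maximum is 130.4 weeks and the SD at most 65.2. Still impossible.
- OTNY's mean of 7.6 months is 33.0 weeks; 89.5/33.0 = 2.7.

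**3. DUP II power at the planned size, all enrollees.** OTNY's SD is not in the documents, so it is assumed. A gamma or lognormal with mean 7.6 and median 5.5 months has SD about 7.2. The largest SD compatible with that mean and median on 0–24 months is 10.02. It needs 50% of patients at exactly 0, 24% at 5.5 and 26% at 24 months, so it is a bound and not a plausible value. A 50% fall is 3.8 months. The smallest detectable fall at 80% power is 2.80 × SE.

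| SD (months) | SE = 0.1274 × SD | Power for 3.8 months | Detectable fall |
|---|---|---|---|
| 7.2 (assumed) | 0.917 | 98% | 2.57 months (34%) |
| 10.02 (bound) | 1.277 | 84.5% | 3.58 months (47%) |

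**4. Hypothesis A as worded.** Sections 8 and 12 expect 4 campaign enrolments per week: 4 × 26/6 = 17.3, about 17 per active cell once the campaign runs everywhere, assuming an even split over clusters. Control cells stay at 32. With 17 per active cell, SE = 0.1492 × SD.

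- Plan's inputs: 0.1492 × 249 = 37.1; 89.5/37.1 = 2.41; power 67%.
- DUP II, SD 7.2: SE 1.074; power 94%; detectable fall 3.01 months (40%).
- DUP II, SD 10.02: SE 1.495; power 72%; detectable fall 4.19 months (55%).

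The Aim 2 power paragraph counts 30 × 12 = 360 enrolled from the campaign part of the design. If all 30 per active cell are campaign admissions, SE = 0.1294 × SD, and DUP II power is 98% and 83%. The plan's campaign count is thus not uniform.

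**The case against.** **The inputs may be for DUP 1.** Antipsychotic treatment is the endpoint named first, and the documents give no OTNY figure for it. This stands: a mismatch for DUP 1 is not shown. What remains is that the plan does not say which DUP is powered.

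**Only the ratio of fall to SD matters, so 80% carries over as a percentage reduction.** It does not carry over exactly, but the error is on the safe side. The plan's ratio is 89.5/249 = 0.36; on OTNY's mean it is 3.8/10.02 = 0.38 at the bounding SD and 3.8/7.2 = 0.53 at the fitted SD. For the all-enrollee comparison by the plan's own method, 768 is enough to detect a 50% fall in DUP II.

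**The all-enrollee reading is an inference.** The plan does not say whose 32 patients are counted. The equal count in every period, and the use of existing OTNY intakes to judge whether the Bronx can reach it, make this the natural reading, but it is not stated.

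A reader might go further and infer that the trial is underpowered, with power down to about 61%. The documents do not support that. The 61% combines the bounding SD, the lower campaign count and a random treatment effect with an SD of 1.9 months, which has no source in the documents; section 12 says only that the effect can be modelled that way. A second tempting reading is dilution. If only the campaign third of intakes, 4/(8 + 4), halve their DUP, the all-enrollee fall is 0.5 × 1/3 = 17%, with power 28% at SD 7.2. That is a different effect assumption from the plan's and does not follow from the 179/249 inputs. Both are illustrative only.

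**Conclusion.** The point holds in a limited form. The sample-size arithmetic is correct. The mean and SD behind it are impossible for DUP II under the two-year onset limit and contradict OTNY's own mean, so the stated 80% is not the power for DUP II. It is not shown to be wrong for DUP 1.

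This is not a finding of inadequate size: for a 50% fall across all enrollees, DUP II power is about 98% at the fitted SD and no lower than 84.5%. The campaign-channel contrast of hypothesis A is less secure: 67% on the plan's own inputs with 17 campaign admissions per active cell, and for DUP II 94% at SD 7.2 or 72% at the bound.

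These DUP II figures assume a 24-month ceiling, ICC 0.1, a fixed treatment effect, one random cluster effect and a normal test. They treat the eligibility onset and the DUP onset as the same date, and the channel figures ignore any selection between channels. With only six clusters the normal test is favourable: a t reference with 10 to 18 degrees of freedom would take the plan's 80.5% to between 72% and 76%.

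**What to change.** In section 12, Aim 1:

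- Name the DUP definition that is powered. If it is DUP 1, give the source of its mean and SD.
- Replace 179/249 weeks and the borrowed ICC with OTNY's mean, SD and cluster ICC for that definition, or with stated ranges if these cannot be obtained.
- Say which contrast is primary: campaign-channel against pre-campaign traditional admissions, or all enrollees before and during the campaign. If the former, give one expected number of campaign admissions per cluster-period, and reconcile the 4 per week with the 30 per active cell used under Aim 2.
- Restate power and the smallest detectable reduction at the planned size for that contrast, under the model that will be used. If the random treatment effect is kept, include it and justify its SD.

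The cost is one rerun of the calculation and some rewording; enrolment need not change. The drawback is reliance on OTNY central for the SD and ICC. Section 12 already provides for its DUP data to reach the research staff; failing that, only a range can be given.

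### The 80% power for Aim 1 needs DUP to fall about 50% on average in every patient group analysed, but the plan does not say whether that group is campaign arrivals or all arrivals

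*Combined protocol and SAP*

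**What the plan says.** Section 12 (Aim 1, Power Analysis) takes a mean DUP of 179 weeks, SD 249 and ICC 0.1 from RAISE-ETP, with 6 clusters and 3 steps. It continues: "Assuming a 50% reduction with our new intervention, the sample size required at 80% power" is 32 per cluster per 6-month period, or 768 in total. It adds: "Power analysis was done only for the primary outcome (hypothesis A").

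Hypothesis A in Sections 4 and 12 reads: "Patients admitted to OTNY via campaign channels will demonstrate a significantly shorter DUP than those admitted to OTNY through traditional outreach" before activation. The Aim 1 text then describes comparing pre-activation DUP with active-phase DUP in patients "arriving both through the campaign as well as through traditional channels". It also says that "all de-identified DUP data routinely uploaded to OTNY central (as part of standard quality improvement) will be provided to research staff for analyses".

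Cell size is judged against current intake: "Based on existing OTNY enrollment data, the Bronx will receive approximately 30 new intakes per 6-month period", and to compensate "we will be collecting DUP data from 40 participants per 6months period in the Manhattan and Brooklyn clusters". OTNY's own mean DUP to enrolment "is reported to be 7.6 months (median 5.5 months"), with no SD.

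The forecasts differ. Sections 5, 8 and 12 (Hypothesis B) expect 8 existing enrolments a week, plus 6 appropriate campaign referrals a week of whom 4 enrol. The Aim 2 power analysis has every appropriate referral enrolling. It then counts 30 per active cell (30 x 12 = 360) from recent OTNY enrolment, which it puts at 26 to 34 per cluster-period. Section 10 (Endpoints) is marked not applicable, so it does not settle the population.

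**The concern.** One power statement stands behind two different contrasts.

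- **Campaign arrivals only.** The 50% could plausibly be the effect per patient, but the group is smaller than total intake and is selected by how patients arrived.
- **All arrivals.** The contrast follows the randomised activation times, but campaign patients are only part of each active cell. A 50% fall among them becomes a smaller average fall unless traditional arrivals improve too.

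The mixed model in Section 12 does not say which active-period patients enter it or whether channel is a term. If the choice is left open, a null primary result could be read as evidence of no effect from a trial said to have 80% power, when the contrast analysed had less. The choice could also be made after the data are seen.

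**Working it through.** **Method.** Cross-sectional stepped wedge (Hussey-Hughes model): 6 clusters, 4 periods, 2 clusters crossing at each step, fixed period effects, random cluster intercept. A cell is one cluster in one 6-month period. For cluster i with cell sizes m_ij:

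V_i = SD² × [ICC × J + (1 − ICC) × diag(1/m_ij)], and Z_i = [period indicators, active indicator].

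SE² is the treatment element of (Σ Z_i' V_i⁻¹ Z_i)⁻¹. Power = Φ(δ/SE − 1.96), plus the small opposite tail. The plan does not state sidedness; two-sided 0.05 reproduces its figure.

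**1. The plan's own figure.** δ = 0.5 × 179 = 89.5 weeks. With 32 in every cell, SE = 31.73 and 89.5/31.73 = 2.82, so power is 80.5%. The exact requirement is 31.55, which rounds up to 32. The smallest fall detectable with 80% power is 2.80 × 31.73 = 88.9 weeks, and 88.9/179 = 49.7%. This is an average over whoever is analysed in the 12 active cells.

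**2. Expected cell sizes.**
- Existing intake: 8 × 26 / 6 = 34.7 per cell (Sections 5 and 8), or about 30 (Aim 2).
- Campaign, 4 a week: 4 × 26 / 6 = 17.3 per active cell if the rate applies once all clusters are active, or 4 × 78 / 12 = 26 if it is an average over the 18-month deployment in Section 9.
- Campaign, 6 a week (all appropriate referrals enrol): 26 or 39 on the same two readings.
- Aim 1's planned cells sum to 30 + 40 + 40 + 3 × 32 = 206 per period. That is close to 8 × 26 = 208 existing enrolments, but not to Aim 2's 6 × 30 = 180.

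**3. Campaign-only contrast**, 89.5-week fall, SD 249, ICC 0.1:

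| Campaign per active cell | Power with 30 / 32 / 34.7 per control cell |
|---|---|
| 17.3 | 66.5 / 67.8 / 69.3% |
| 26 | 75.2 / 76.5 / 78.0% |
| 30 | 78.1 / 79.3 / 80.8% |
| 39 | 82.9 / 84.1 / 85.5% |

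About 30 per active cell is needed for 80%.

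**4. All-channel contrast**, all forecast enrollees analysed. Average fall = 50% × [share + (1 − share) × s], where share is the campaign share of active-period enrollees and s is the effect on traditional arrivals as a fraction of the campaign effect (spillover). The plan gives no s; 0 and 0.5 are assumptions.

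| Existing + campaign per active cell | Share | Average fall, s = 0 | SE | Power, s = 0 | Power, s = 0.5 | Detectable fall at 80% |
|---|---|---|---|---|---|---|
| 34.7 + 17.3 | 33% | 16.7% | 27.72 | 19% | 58% | 43% |
| 34.7 + 26 | 43% | 21.4% | 26.75 | 30% | 67% | 42% |
| 34.7 + 39 | 53% | 26.5% | 25.60 | 46% | 76% | 40% |
| 30 + 17.3 | 37% | 18.3% | 29.39 | 20% | 55% | 46% |
| 30 + 26 | 46% | 23.2% | 28.28 | 31% | 64% | 44% |
| 30 + 39 | 57% | 28.3% | 26.99 | 47% | 74% | 42% |

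With 34.7 existing per cell, 80% power needs s = 0.80, 0.72 or 0.58 at shares of 33%, 43% or 53%.

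**5. OTNY scale.** Mean 7.6 months, so a 50% fall is 3.8 months. The SD is not stated; 5 to 10 months is assumed. About 10 is the most that a 0-24 month range allows with that mean and median, the range being suggested by the two-year onset criterion in Section 7. Results with 34.7 existing per cell, from SD 5 to SD 10:
- Campaign-only at 17.3 per active cell: 99.9% down to 74%.
- All-channel, 33% share: 62% down to 21% with s = 0, and 99.5% down to 62% with s = 0.5.
- All-channel, 53% share, s = 0: 97.5% down to 50%.

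**The case against.** The best reply is that the powered population is named. Hypothesis A has the same meaning in both places, the plan says only that hypothesis was powered, and the sentence mentioning both channels may just describe the data to be shown, channel by channel. With the 30 per active cell used for Aim 2, campaign-only power is 78-81%, close to the stated figure.

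The reading is possible, but it does not secure the 80%. Aim 2's 30 per cell comes from existing OTNY enrolment and is not a campaign forecast. The stated 4 a week gives 17 or 26 per active cell. Only the 6-a-week figure averaged over 18 months (39 per cell) passes 80%, and it conflicts with 4 of 6 enrolling.

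Other parts of the reply stand. The low all-channel figures need pooled channels, no spillover and the RAISE-ETP SD all together. The 32 is a required number, not a stated cap on the analysis. Clusters are randomised, not patients. DUP is analysed in people who enrol, and Hypothesis B expects enrolment to rise, so the all-channel group is also formed after randomisation.

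**Conclusion.** The point holds and should be fixed. The plan does not say which population is primary for Aim 1 or to which one the 50% applies, and its 4-a-week forecast does not secure 80% power for either on the stated inputs. Campaign-only power is about 67-69% or 75-78%. All-channel power over the full range of forecasts is about 19-47% without spillover and 55-76% with half spillover.

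A reader might infer two stronger conclusions that the documents do not support:

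- **That 32 is miscalculated.** It is correct for its inputs. If the 50% is meant as the overall fall in the analysed group, 32 per cell is enough.
- **That the trial has only about 20% power.** That needs zero spillover, on which the plan is silent, and an SD of 249 weeks, which is far from OTNY's scale. On the OTNY scale either contrast can reach 80% under favourable assumptions, and either can miss it.

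All figures assume a fixed treatment effect. The random treatment effect that Section 12 allows would require more patients. The unreconciled populations do not depend on any of these ranges.

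**What to change.** In Section 12:

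1. Make the primary Aim 1 comparison all OTNY enrollees by cluster-period, classified by campaign activation, since this follows the randomisation of clusters. Note that the mix of enrollees may still shift because the campaign is expected to raise enrolment. Confirm that all the DUP data supplied will be analysed, not 32 or 40 per period.
2. If the campaign-channel contrast is kept, label it secondary and non-randomised, and give its expected number per active cell.
3. Reconcile the campaign forecasts (4 a week, all appropriate referrals enrolled, 360) and the intake figures (8 a week, 26 to 34 per cell, 40 in Manhattan and Brooklyn). Say whether the weekly rate assumes full activation.
4. Replace the single 80% with power over stated ranges of campaign share (about 33-57%), spillover and an OTNY-based SD. Alternatively, give the smallest overall reduction detectable with 80% power. At SD 249 that is about 50% at 32 per cell and about 40-46% with all forecast enrollees.

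The cost is protocol wording and a less favourable stated power. No extra patients or data are needed.

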8. NUMBER OF SUBJECTS

- Indicate the total number of subjects to be accrued locally. If applicable, distinguish between the number of subjects who are expected to be pre-screened, enrolled (consent obtained), randomized and complete the research procedures.
- If your study includes different cohorts, include the total number of subjects in each cohort.
- If this is multisite study, include total number of subjects across all sites.

OTNY receives on average 34 referrals weekly, of which, on average 26% are found eligible, and 8 new FEP patients are enrolled in NYS each week. Based on existing OTNY inquiry data as well as the results of our prior pilot initiatives, we anticipate approximately doubling weekly inquiries as a result of the campaign, arriving through campaign related channels over the course of the trial (30 additional referrals). Of those, we anticipate that 20% will be appropriate for OTNY (6 participants weekly) and that 4 of those individuals will be successfully enrolled each week as a result of the campaign.

Version Date: 6.9.22 Page 9 of 31

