each will target a dedicated audience based on demographics (age) and online search query. For example, "I am hearing voices" will generate the participant ad/campaign, while "my daughter is acting strange" will generate an entirely different set of ads geared towards caregivers. Power Analysis: Current OTNY referral data suggest that caregivers including parents are 5 times more likely to initiate a referral inquiry as compared to prospective participants themselves. We therefore anticipate that at least 2/3 (66.7%) of campaign referrals (approximately 20 weekly) will be generated by the parent campaign. Based on OTNY referral data, we anticipate that 20% will be appropriate and all will be enrolled into OTNY. Sample size necessary to detect a prevalence of 66.7% for the caregiver campaign compared to the null hypothesis of equal rates for the two campaigns is 68, which has to be multiplied by the design effect (variance inflation factor), [1 + (n-1)p], to get required sample size. As ICC (p) ranges from 0.01 to 0.06, the design effect will range from 1.67 to 5.02 and the sample size required will vary from 114 to 342. Although there are 24 six-month time periods from all clusters (4 per cluster and 6 clusters, $4 \times 6 = 24$) based on the stepped wedge design for Aim 1, only 12 of them will have the campaign. Based on recent OTNY referral data, the number of enrolled subjects per cluster in a 6-month period varied from 26 to 34, with an average of approximately 30. Thus, we expect to have (30 x 12) 360 subjects enrolled from the campaign part of the stepped wedge design. This sample size will be sufficient to detect the hypothesized difference in rates (66.7% vs. 33.3%) at 80% power and α = 0.05, with an ICC as high as 0.06.

Aim 3: Explore which methods of online engagement are most effective at promoting treatment initiation by comparing rates of OTNY enrollment of individuals interacting with research staff via live chat or two-way video to rates of enrollment of individuals utilizing text, email, and/or phone alone. Hypothesis: individuals with FEP who engage via two-way video or live chat will be significantly more likely to initiate in-person contact compared to individuals with FEP who engage via text, email, and/or phone alone.

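### The Aim 1 enrolment figures conflict: 40 per period in Manhattan and Brooklyn exceeds the plan's own reported range of 26 to 34, and 768 matches no set of expected counts

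*Combined protocol and SAP*

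**What the plan says.** Section 12, Aim 1 power analysis, states that "the sample size required at 80% power and α = 0.05, is 32 participants per 6-month period per cluster", and multiplies this over 4 periods and 6 clusters to reach 768. It expects the Bronx to fall slightly short, at about 30 per period, and compensates: "we will be collecting DUP data from 40 participants per 6months period in the Manhattan and Brooklyn clusters". It does not distinguish control from active periods. The same Aim 1 text says that "all de-identified DUP data routinely uploaded to OTNY central" will be given to the research staff for analysis.

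Section 12, Aim 2 power analysis, reports from recent OTNY data that "the number of enrolled subjects per cluster in a 6-month period varied from 26 to 34, with an average of approximately 30". It uses 30 for each of the 12 campaign cells, giving 360.

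Sections 5 and 8 state that "8 new FEP patients are enrolled in NYS each week" and expect the campaign to add 4 enrolments a week.

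**The concern.** Section 12 treats the Bronx as the one short cluster and covers it with a surplus from two larger ones. The Aim 2 paragraph makes about 30 the average for all clusters and puts the top of the recent range at 34. The Bronx is then typical, and the clusters meant to compensate have no such surplus before the campaign starts. The weekly figure in Sections 5 and 8 points the other way, to an average above that same maximum.

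DUP under hypothesis A is the only outcome with an Aim 1 power analysis. If its cell counts come from figures that cannot all be true, a reader cannot tell what sample the trial expects or what power goes with it. The plan also does not say whether 32 and 40 are minimum targets or fixed numbers, so the size of the analysis set is left open.

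**Working it through.** **Inputs (Section 12 unless noted).** The DUP mean "was 179 weeks (SD = 249), and the ICC used for the original power analysis for the RAISE study was 0.1". "Assuming a 50% reduction with our new intervention" gives a difference of 0.5 × 179 = 89.5 weeks, or 89.5/249 = 0.359 SD. For the design, "a fixed number of clusters (6) and number of steps (3) was specified based on feasibility", with 4 periods. I assume two clusters per step, which agrees with the plan's 12 campaign cells (2×3 + 2×2 + 2×1 = 12). Alpha is taken as two-sided 0.05; the plan does not state sidedness, but this reproduces its figure.

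**1. Reproducing 32.** Individual randomisation needs 2 × [249 × (1.960 + 0.842)/89.5]² = 121.5, so 122 per arm and 244 in total. The stepped-wedge design effect for k = 3 steps, one baseline period and ICC ρ = 0.1 is

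DE(m) = [1 + ρ(km + m − 1)] / [1 + ρ(km/2 + m − 1)] × 3(1 − ρ) / [2(k − 1/k)].

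At m = 32: 13.7/8.9 × 2.7/5.333 = 0.779. Then 244 × 0.779 / 6 = 31.7, which rounds up to 32. The plan's figure reproduces.

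**2. Counts per period.**

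| Basis | Per 6-month period, all clusters | Over 4 periods |
|---|---|---|
| Requirement, 32 in each cluster | 6 × 32 = 192 | 768 |
| Stated pattern (Bronx 30, Manhattan and Brooklyn 40, other three 32) | 30 + 40 + 40 + 32 + 32 + 32 = 206 | 824 |
| Aim 2 average, 30 in each cluster | 6 × 30 = 180 | 720 |
| Sections 5 and 8, 8 a week, no campaign | 8 × 26 = 208 (34.7 per cluster) | 832 |

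The offset is also out of proportion. The Bronx is short by 2 × 4 = 8 records, and the two larger clusters are to add 8 × 2 × 4 = 64. The net 56 is the gap between 768 and 824.

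**3. Control periods in Manhattan and Brooklyn.** A cluster has 1, 2 or 3 control periods according to its step, so the two together have 2 (both at step 1) to 6 (both at step 3). Even at the reported maximum of 34, each of these cells is 40 − 34 = 6 short, or 12 to 36 in all.

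**4. Active periods.** Four extra enrolments a week are 4 × 26 / 6 = 17.3 per active cell if spread evenly, so about 47 on a base of 30. The plan thus carries three values for an active cell: 30 (Aim 2), 32 or 40 (Aim 1), and about 47 (implied by Section 8).

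**5. Power.** The model has a random cluster intercept and fixed period effects. With equal cells,

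Var = 6s(s + 4t) / [16s + 40t], with s = 0.9 × 249²/m and t = 0.1 × 249² = 6200.1.

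The constants follow from 12 active cells, squared period totals 0 + 4 + 16 + 36 = 56 and squared cluster totals 2(9 + 4 + 1) = 28: 6×12 − 56 = 16, and 12² + 6×4×12 − 4×56 − 6×28 = 40.

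- m = 32: s = 1743.8, SE = 31.73, power = Φ(89.5/31.73 − 1.96) = 80.5%.
- m = 30: s = 1860.0, SE = 32.73, power = Φ(89.5/32.73 − 1.96) = 78.1%.

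Unequal cells were computed by generalised least squares over all 90 allocations of six clusters to three steps:

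| Control cell | Active cell | Power |
|---|---|---|
| 32 | 32 | 80.5% |
| 30 | 30 | 78.1% |
| Stated pattern | Stated pattern | 82.3% to 83.4% |
| 30 | Stated pattern | 79.5% to 81.7% |
| 30 | 47.3 | 86.1% |

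**The case against.** The range of 26 to 34 contains 32, so individual control cells can reach the requirement; only the average falls below it. The figures are approximate and describe past enrolment. On 8 a week, 208 per period just covers the stated pattern of 206 in aggregate, and 768 is a required size rather than a forecast. Power stays close to 80% in most scenarios. All of this stands, and it limits the point. It does not remove it, because the plan's feasibility turns on which of two incompatible figures is right. Aggregate cover also does not show that the two named clusters can supply 40 each.

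A reader might go further and infer that 32 and 40 act as caps, so that the plan discards active-period records or lets someone choose among them. The documents do not support this. No section sets a cap, a sampling rule or an exclusion beyond those counts. The 32 is presented as a required size, 40 is an upward adjustment, and all uploaded DUP data are to be provided for analysis, with both referral channels included. At most, the status of the two numbers is unstated.

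The 86.1% should not be read as a secure gain either. It gives every active-cell enrollee the full 50% reduction. If only the 17.3 of 47.3 who came through the campaign benefited, the average effect would be about 37% of that assumed (32.8 weeks) and power about 20%.

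**Conclusion.** The point holds as an inconsistency in the stated counts. On the Aim 2 range, 40 per period is not available in Manhattan and Brooklyn before activation, and 32 is not reached on average. The weekly figure in Sections 5 and 8 exceeds that range, and 768 matches neither the stated pattern nor 30 per cell.

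The consequence for power is small on the plan's inputs: about 2 points lost if every cell has 30, about none if only control cells do, and about 86% if active cells reach 47. These results assume the RAISE mean, SD and ICC, two clusters per step, an even spread of the extra enrolments, and a 50% reduction for all active-cell enrollees. They say nothing about whether those planning values suit OTNY, whose mean DUP the same section gives as 7.6 months.

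**What to change.** In Section 12, replace the 40 and the total of 768 with one table of expected enrolment per cluster, separately for control and active periods. Take it from a single reconciled source, and bring Sections 5 and 8 and the Aim 2 paragraph into line with it. Restate Aim 1 power from those counts.

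Add a sentence saying that 32 is a planning minimum and that all OTNY enrollees with a DUP record in the 24 cluster-periods are analysed.

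The cost is wording, a per-cluster extract of enrolment data that OTNY already holds, and one power calculation. Design and data collection do not change.
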